4.8. Primary Endpoint Analysis

Study MTAE has a 76-week common close design where all enrolled participants continue on study drug and complete study assessments until last enrolled participant that has not discontinued reaches 76 weeks of double-blind treatment. The maximum duration of treatment is 124 weeks. The analysis in this section will be conducted in the moderate tau study population.

4.8.1. Main Analytical Approach

The primary objective of this study is to test the hypothesis that LY3372689 slows cognitive and functional decline in early symptomatic AD participants with moderate cortical tau burden as measured by iADRS compared with placebo through end time point (76-124 weeks). This will be assessed using a DPM, evaluating possible slowing of disease progression with treatment of LY3372689 relative to placebo.

The main purpose of the DPM is to estimate a quantity known as the disease progression ratio (DPR), which measures the proportion of disease progression in active treatment arms relative to placebo arm. The iADRS score at baseline and each scheduled postbaseline visit (according to SoA) during the treatment period will be the dependent variable. The DPM is as follows:

$$Y_{ij} = 1_{j>0} \cdot e^{\theta_{T_i}} \sum_{v=1}^j \alpha_v + X_i \beta + \gamma_i + \varepsilon_{ij}, i = 1, 2, \dots, k; j = 0, 1, 2, \dots, l$$

where Y_{ij} denotes the clinical outcome at visit j for participant i , clinical outcome scores at baseline (prior to treatment) is Y_{i0} . The term $1_{j>0}$ is the indicator function that is 0 for $j = 0$ (baseline visit) and 1 otherwise. For post-baseline visits, the multiplication term $e^{\theta_{T_i}}$ is the DPR associated with the treatment group of participant i , $T_i \in \{\text{Placebo}, \text{LY}_{\text{low}}, \text{LY}_{\text{high}}\}$. $\theta_{\text{Placebo}} = 0$, $e^{\theta_{\text{LY}_{\text{low}}}}$ and $e^{\theta_{\text{LY}_{\text{high}}}}$ represent the DPR of the low dose and the high dose in relative to placebo, respectively. α_v ($v \geq 1$) denotes the mean change of placebo response from visit $v - 1$ to visit v . The parameter γ_i represents a subject-specific random intercept for participant i which is assumed to center the baseline main effect $\gamma_i \sim N(\mu_{BL}, \sigma_{BL}^2)$, where the parameter μ_{BL} models the mean baseline score across arms. ε_{ij} is the error variance which is assumed to follow $\varepsilon_{ij} \sim$

$N(0, \sigma^2)$. X_i denotes subject specific baseline covariates that will be included in the model and β represent the associated fixed effects. Stratification variables used for randomization such as investigator site (pooled) will be included in the model. Baseline covariates such as age and concomitant AChEI/memantine use at baseline (yes/no) will also be included in the model.

The DPM model assumes the treatment effect of LY3372689 is proportional to placebo over the course of the study. This proportionality assumption is similar to the assumption made in proportional hazards modeling of time to event data. The DPM includes generally diffuse priors on all parameters in the model. The precision value for the prior distribution of all parameters is set to a small value; therefore, the prior distributions on all parameters have very little impact on the posterior distributions. No information or knowledge of the effect of LY3372689 from previous studies will be incorporated into the prior distributions, and the inference will be based on Study MTAE only. The specifications of the prior of the model parameters are as following:

A diffuse normal prior is assumed for μ_{BL} and a diffuse inverse gamma prior is considered for the variance of the participant-level random intercept σ_{BL}^2 :

$$\mu_{BL} \sim N(0, 10^4), \sigma_{BL}^2 \sim IG(0.005, 0.005).$$

The same diffuse normal prior distribution is assumed for each change in the placebo mean disease progression from visit $v - 1$ to visit v , α_v :

$$\alpha_v \sim N(0, 10^4)$$

A prior distribution of $N(0, 0.25)$ is assumed for the log(DPR) parameter of each active treatment arm (LY_{low} and LY_{high}).

A diffuse prior of the following form is also assumed for β , the fixed effect of the baseline covariates.

$$\beta \sim N(0, 10^4)$$

An inverse gamma prior $\sigma^2 \sim IG(0.005, 0.005)$ is assumed.

A DPR less than 1 corresponds to a slowing of disease progression (i.e., favoring LY3372689); similarly, a DPR greater than 1 reflects some evidence of cognitive worsening (i.e., favoring the placebo). The null hypothesis is that the DPR of both active treatment arms equal to 1.

A DPR less than 1 corresponds to a slowing of disease progression (i.e., favoring LY3372689); similarly, a DPR greater than 1 reflects some evidence of cognitive worsening (i.e., favoring the placebo). The null hypothesis is that the DPR of both active treatment arm equal to 1.

The Bayesian inferences will be summarized including posterior distribution of DPR and posterior probabilities of meeting various DPR thresholds of interest (e.g., 0.75 which translates to 25% slowing of disease progression with LY3372689 group versus placebo). Bayesian posterior probability of at least one active treatment arms being superior to placebo by at least a margin of interest (change from baseline in iADRS score between treatments equivalent to a 25% slowing of disease progression relative to placebo) will also be calculated.

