3	10Jun2024	
Section 3: removed Biomarker Evaluable Set and the non-programmable item in per-protocol definition.
 
Section 4.5: added a few more variables to be included in baseline demographic table.
 
Section 4.8: added effect of interest for DPM analyses; updated sensitivity analysis for more specific details regarding timepoints being included.
 
Section 4.9.2 to Section 4.9.3: updated with more details.
 
Added Section 4.11.2 and Section 4.11.3: analyses for Digital Clock Drawing Test. Digit Symbol Substitution Test, time to progression based on CDRGS
	For clarity, completeness, accuracy, and flexibility in less priority analyses.
		Section 4.11.1: Updated Analysis of Blood-based biomarkers	Updated per amendment (c).
		Section 4.12.1: removed 'prior use approved DMT subgroup analysis'	Little value given very few (<5) enrolled participants enrolled in this subgroup.

		Removed covariate adjustment for 'prior or current use of any approved disease-modifying therapy for AD'	
		Section 4.8.3: Removed NCS3, per-protocol, completer analyses. Removed Bayesian Analysis with Shared Control Removed Health Outcome and Quality of Life analyses.	No longer of interest or not applicable.
4	19Jul2024	Section 2: modified the language to add clarity.	For clarity
		Section 4.9.2.1: Removed the pre-specified probability thresholds associated with the graphical testing scheme to control the two-sided Type I error at 0.05 level due to the rationale provided on the right. Instead, the methodological approach for how probability thresholds will be calculated is pre-specified.	Subsequent Simulation has revealed the thresholds in the graphical testing scheme may be sensitive to the underlying assumption of the placebo trajectory and variance-covariance matrix with the Bayesian DPM. The methodological approach that was used to calculate the probability thresholds was also modified to maintain the consistency with the data generation mechanism as the sample size determination (as described in Section 5).
		Correction to the V3 History where it stated 'Section 4.9.2 to Section 4.9.3: updated with more details. Added key secondary analyses to graphical testing scheme.' The key secondary analysis was not added to graphical testing scheme in the V3 amendment.	Error correction.
5	20Jun2025	Section 3. Added two analysis set: Safety Follow-up, Efficacy Follow-up	Analyses for data that are collected during Study Period 3 and 4 (Post-

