1.3. Method of Assignment to Treatment

This is a double-blind study, with design to maintain blinding to treatment. To preserve the blinding of the study, a minimal number of Lilly personnel will see the randomization table and treatment assignments before the study is complete.

Participants who meet all criteria for enrolment will be assigned a study (patient) number at Visit 601 or Visit 1 and randomized to double-blind treatment at Visit 2. Participants will be randomized to LY3372689 or Placebo in a 1:1:1 ratio. For between-group comparability, patient randomization will be stratified by investigative site and tau burden (moderate versus high), and by prior or current use of any approved disease-modifying therapy for AD.

Assignment to treatment groups will be determined by a computer-generated random sequence using an interactive web response system (IWRS). Randomization into one stratum may be discontinued at the discretion of the sponsor. LY3372689 will be made available in blister packaging and will be given by a blinded nurse or other qualified blinded personnel, as described in the pharmacy manual. Site personnel will confirm that they have located the correct packages by entering a confirmation number found on the label into the IWRS.

For the first approximately 30 participants, the IWRS will be programmed to guarantee balance between the arms for the first interim analysis for safety; this is referred to as the burn-in period. After the burn-in period, participant randomization will then follow the dynamic allocation (minimization) method of Pocock and Simon (1975) to balance the treatment arms using investigative site as a factor. This is to ensure balanced participant assignment between treatment arms within each site at the end of the study.

2. Statistical Hypotheses

The primary efficacy analysis will be a Bayesian DPM conducted on the primary outcome iADRS. The primary efficacy analysis population will be those with moderate levels of tau pathology at baseline. A critical success factor (CSF) will be established of the following form:

- Probability (at least 25 % slowing of disease progression with LY3372689 relative to placebo) > 0.6 .

The Bayesian DPM will be utilized to calculate the posterior probability of at least 25% slowing. If the posterior probability exceeds the probability threshold for at least one LY3372689 versus placebo comparison, the trial will have been considered to have met its primary endpoint.

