4.8.2.1. Natural Cubic Spline (NCS) Analysis

A NCS model with 2 degrees of freedom (NCS2) (Donohue et al. 2023) will be used to estimate the difference in the change in iADRS score between the treatment arms. The NCS2 model has 3 knots over the observation time will be placed: 2 at the boundaries (minimum and maximum observation time), and 1 internal knot at the median observation time. The baseline estimates are restricted to be the same for all treatment arms. The model will be estimated using restricted maximum likelihood method (RMLE).

The iADRS score at baseline and at each of the scheduled post-baseline visits (according to SoA) will be included in model as a dependent variable. The analysis model will include the fixed effects of NCS basis expansion terms (two terms), NCS basis expansion term-by-treatment interaction (two terms), age at baseline, AChEI/memantine use at baseline (yes/no), and investigator site (pooled). Visit will be treated as a continuous variable with values equal to weeks between baseline and post-baseline exam dates, and the NCS basis function will be derived using these visits in weeks. An unstructured variance-covariance structure matrix will be used to model within-subject variance-covariance of residual errors across visits where visits are modeled as a categorical variable. If the unstructured variance-covariance structure matrix results in a lack of convergence, the following structures will be used in sequence:

- Heterogeneous Toeplitz covariance structure
- Heterogeneous autoregressive order 1 covariance structure
- Heterogeneous compound symmetry covariance structure, and
- Compound symmetry covariance structure

Mean change from baseline values, and the comparisons between change from baseline values by treatment arms will be estimated through the proper contrast set up. The Kenward-Roger approximation will be used to estimate the denominator degrees of freedom.

Percent slowing comparing to placebo group will be calculated as the least-squares (LS) estimates of differences in change from baseline between treatment groups, then divided by the LS estimates of mean change from baseline value from placebo group. A 95% CI for this percent slowing is calculated based on a Delta method (Beyene et al. 2005).

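### The primary disease progression model has no term for participants declining at different rates, so its posterior for the progression ratio is too narrow if they do

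*SAP*

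**What the plan says.** SAP 4.8.1 models the iADRS at all visits jointly: "The iADRS score at baseline and each scheduled postbaseline visit (according to SoA) during the treatment period will be the dependent variable". Two terms carry the variation that the mean model leaves over. One "represents a subject-specific random intercept for participant"; the other "is the error variance which is assumed to follow" a normal distribution with mean zero and a single variance. Only one prior is given for that variance: "An inverse gamma prior $\sigma^2 \sim IG(0.005, 0.005)$ is assumed". There is no random slope, visit-specific variance or serial correlation. Protocol 9.4.2 likewise has one subject-specific random effect.

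The other iADRS models are treated differently. For NCS2, SAP 4.8.2.1 states: "An unstructured variance-covariance structure matrix will be used to model within-subject variance-covariance of residual errors across visits". The MMRM in 4.8.2.2 also starts from an unstructured matrix. In both, compound symmetry is the last of four fallbacks if the fit does not converge.

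SAP 4.9.2.1 sets the two iADRS probability thresholds for the testing graph. It simulates null data with the NCS2 covariance, then fits the 4.8.1 model to them. Separately, SAP Section 2 has a fixed success rule: "Probability (at least 25 % slowing of disease progression with LY3372689 relative to placebo) > 0.6".

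**The concern.** The DPM estimates a ratio of progression rates, but lets participants differ only in starting level. With a random intercept and independent errors, the model takes the variance of change from baseline to be the same at Week 12 as at Week 76. If some people decline quickly and others slowly, that variance grows with time. The later visits of one person then share the same slope deviation, yet the model counts them as nearly independent evidence on progression. The posterior becomes too narrow.

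SAP 4.8.1 promises the posterior of the DPR and probabilities at several DPR thresholds, and readers will take these at face value. The same model is applied, without any calibration, to iADRS in the full population (4.9.1), to CDR-SB, ADAS-Cog13, ADCS-iADL and MMSE (4.9.2), and to the DSST and digital clock test (4.11.2).

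**Working it through.** **The plan's own figure.** SAP Section 5 gives a false-positive probability of about 2.4%. It cannot be reproduced: the placebo trajectory, the variances and the moderate-tau sample size are redacted or not stated. If the criterion is the 0.6 rule for one dose, it passes when the log DPR estimate falls below log 0.75 − 0.2533·SE. Setting that probability to 2.4% (z = −1.977), ignoring the prior, gives SE = 0.2877/(1.977 − 0.2533) = 0.167. This shows only the order of magnitude.

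**What the model implies.** Under 4.8.1, Var(Y_ij − Y_i0) = 2σ² at every visit. With a random slope of SD s per 76 weeks it is 2σ² + s²(t/76)². Suppose the SD of 76-week change is 12 (variance 144) and slopes account for half of it. The variance is then 72 + 72·(12/76)² = 73.8 at Week 12 and 144 at Week 76. The DPM must use one value for both.

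**Assumptions for the size.** None of these comes from the documents except the visit schedule and the prior:
- 80 per arm; visits at Weeks 0, 12, 24, 36, 52, 64, 76 and 88
- 25% dropout by Week 76, and half of completers with Week 88 data
- baseline SD 13, SD of 76-week change 12, placebo decline 10 points, true DPR 1
- slope share of the 76-week change variance: 0, 25, 50 or 75%
- the log DPR prior ("A prior distribution of $N(0, 0.25)$ is assumed for the log(DPR) parameter of each active treatment arm") read as variance 0.25

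**Simulated null trials.** Posterior SD is the model's own average for log DPR. Sampling SD is the actual spread of the estimates.

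| Slope share (slope SD) | SAP model: posterior SD / sampling SD | 95% coverage | Correct covariance: posterior SD / sampling SD | 95% coverage |
|---|---|---|---|---|
| 0% (0) | 0.135 / 0.131 | 96% | 0.136 / 0.131 | 96% |
| 25% (6.0) | 0.125 / 0.153 | 90% | 0.153 / 0.146 | 97% |
| 50% (8.5) | 0.113 / 0.170 | 81% | 0.165 / 0.156 | 96% |
| 75% (10.4) | 0.099 / 0.188 | 70% | 0.175 / 0.163 | 97% |

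The shortfall in posterior SD is 1 − 0.125/0.153 = 18%, 1 − 0.113/0.170 = 34% and 1 − 0.099/0.188 = 47%. Across the variants run (60 or 80 per arm, decline 10 to 14), the ratio of sampling to posterior SD was 1.14–1.25, about 1.4–1.5 and 1.9–2.0. It hardly depended on sample size or decline. As slope share rises, the SAP model's posterior SD falls while the real sampling SD rises.

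**Check.** Coverage should be close to 2Φ(1.96 × posterior SD / sampling SD) − 1. At 50% this is 2Φ(1.96 × 0.665) − 1 = 81%. A separate calculation comparing model-based and sandwich variances gives 96%, 90%, 80% and 69%. It has posterior against sampling SD of 0.136 against 0.130 at share 0, and 0.098 against 0.190 at 75%.

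**Efficiency.** Sampling SD under the SAP model relative to the correct covariance is 0.153/0.146 = 1.05 at 25% and 0.170/0.156 = 1.09 at 50%. At 75% it is 0.188/0.163 = 1.15, or 0.190/0.163 = 1.17 by the sandwich calculation.

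**The 0.6 rule.** The fits above use posterior modes. Full MCMC on eight data sets gave similar SDs (about 0.13 against 0.13 with no slopes, 0.12 against 0.11 at 50%) but means 0.03 to 0.10 lower on log DPR. With an approximate correction for that shift, the null pass rate for either dose is 3.0, 7.1, 8.7 and 13.4% with the SAP model. With the correct covariance it is 3.0, 7.0, 9.3 and 12.3%.

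**The case against.** The strongest reply is that the plan already deals with the misspecification where a formal claim is made. SAP 4.9.2.1 generates null data from the NCS2 covariance, fits the same random-intercept DPM and reads the threshold from the simulated tail. A reader might infer from the narrow posterior that type I error is uncontrolled at the moderate-tau iADRS nodes. The documents do not support that, and this part of the reply stands.

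A reader might also expect a better covariance to repair the fixed 0.6 rule. It would not. A cutoff of 0.6 lies close to the posterior median, so its error rate depends mainly on the true sampling variability and on how far the placebo arm declines. Uncorrected posterior modes do suggest an improvement (6.7% against 3.3% at half share), but the gap disappears once the shift towards lower DPR is allowed for. Nor does either document declare success on a posterior probability that the DPR is below 1, so a false-positive rate for such a rule would not describe this trial.

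A third inference is that compound symmetry explains why, as the SAP version history puts it, "the thresholds in the graphical testing scheme may be sensitive to the underlying assumption of the placebo trajectory and variance-covariance matrix". That is unproven. The SAP names the placebo trajectory as well, and thresholds move under a correct model too. With the right covariance and a decline of 10, the per-dose threshold for 2.5% runs from 0.54 to 0.76 as slope share rises from 0 to 75%. With the SAP model it runs from 0.53 to 0.88.

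Finally, NCS2 reports percent slowing with a 95% confidence interval under an unstructured covariance, which gives readers a sounder counterpart. That limits the harm. It does not correct the primary model's own posterior, and the SAP gives no warning that the two may differ in stated precision.

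**Conclusion.** The structural point is exact: the primary DPM assumes compound symmetry, and the SAP does not assume it as the starting point for its other models of the same score. The direction follows: if rates of decline differ between participants, the DPR posterior is too narrow.

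The size depends on a slope variance that the documents do not give. Over the assumed range of 25%, 50% and 75% slope share, the posterior SD is about 15%, 35% and 50% too small, and 95% intervals cover about 90%, 80% and 69%. With no slope variation there is no problem. The sampling SD is also about 5 to 17% larger than it need be. Coverage is used here as a measure of calibration; the SAP promises the posterior and threshold probabilities rather than a named 95% credible interval.

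The harm is confined to the iADRS posterior and its threshold probabilities, and to the uncalibrated DPM analyses of the key secondary, other secondary and exploratory scales. Size was worked out for iADRS only. The formal test at the moderate-tau iADRS graph nodes is protected, and the 0.6 rule is a separate matter that this change would leave almost as it is.

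**What to change.** In SAP 4.8.1, add a participant-level random slope on progression, with a stated prior. A heterogeneous or unstructured residual covariance would also serve. It would need its own priors and a selection rule, because the fallback list for NCS2 and MMRM is triggered by non-convergence of a likelihood fit and does not carry over directly to MCMC. Sparse late visits, which SAP 4.1 admits with little more than 10 observations per arm, also favour the random slope.

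Fit the same model in step 3 of the 4.9.2.1 threshold simulation, and use it wherever 4.9.1, 4.9.2 and 4.11.2 call the DPM. Keep the random-intercept DPM as a prespecified sensitivity analysis. If unblinding has already occurred, report the richer DPM beside the prespecified one, label it post hoc, and caution against reading the prespecified posterior probabilities at face value.

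The cost is SAP text, longer run time for the 100,000 calibration fits, and somewhat wider intervals.

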where Y_{ij} denotes the clinical outcome at visit j for participant i , clinical outcome scores at baseline (prior to treatment) is Y_{i0} . T_i denotes the treatment arm for participant i . The parameter γ_i ($i=1, 2, \dots, k$) represents the subject-specific random effect for participant i . e^{θ_T} is the disease progression ratio (DPR) for treatment T and $e^{\theta_T} = 1$ for placebo; e^{θ_1} and e^{θ_2} represent the DPR of the low dose and the high dose, respectively. The parameter α_v is the mean change of placebo response from visit $v-1$ to v . ε_{ij} is the error term. Any stratification variables used for randomization such as investigator site and prior or current use of any approved disease-modifying therapy for AD will be included in the model. Baseline score, baseline age, concomitant acetylcholinesterase inhibitor (AChEI)/memantine use (yes/no) will be included in the model as well. Diffuse priors will be used for the Bayesian inferences in the DPM analysis. A DPR less than 1 corresponds to a slowing of disease progression; similarly, a DPR greater than 1 reflects some evidence of cognitive worsening. The DPM will be fitted to the data and Bayesian inferences will be summarized including posterior distribution of DPR and posterior probabilities of various DPR thresholds of interest (e.g., 0.75 which translates to 25% slowing of disease progression with LY3372689 group versus placebo). The null hypothesis is that the DPR between the LY3372689 group versus placebo equals 1.

The primary endpoint will also be assessed using natural cubic spline model with degrees of freedom 2 (NCS2) and MMRM to serve as sensitivity analyses. Additional models/analyses may be considered if deemed appropriate. The SAP will describe the planned analyses in greater details.

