4.15.2. Participant Characteristics

4.15.3. Listing and summary table will be provided for the Efficacy Follow-up Analysis Set. Refer to Section 4.5 for details. Analyses of Clinical and Biomarker Endpoints

The analyses of clinical and biomarker endpoints will include safety follow-up baseline (defined as the last available visit from V21 to V29 during the double-blinded period), V802, and V803. These analyses will be performed using the Efficacy Follow-up Analysis Set.

[figure not shown]
Listings and box plot will be provided for the following endpoints, if deemed appropriate.

- Clinical endpoints: iADRS, CDRSB, ADAS-Cog13, ADCS-ADL, and MMSE
- Biomarker endpoints: volumetric MRI (Hippocampal volume (mm³) and Whole brain volume atrophy (cm³)), blood-based biomarkers (plasma P-tau217, NfL, and GFAP)

Changes from both safety follow-up baseline and the original baseline at V802 and V803 will be assessed using MMRM. The analysis model includes the fixed effects of treatment, visit as a categorical variable, treatment-by-visit interaction, baseline score, and baseline score-by-visit interaction. Baseline covariates such as age, AChEI/Memantine use, pooled investigator and tau PET category will be included in the model.

5. Sample Size Determination

Approximately 330 participants will be enrolled and randomized in a 1:1:1 ratio to the 3 treatment arms (placebo and 2 active arms of LY3372689). It is expected that approximately 240 participants (i.e., 75%) will complete the double-blind Period 2a 76-week treatment period of the study (approximately 80 per treatment arm). Using a DPM model over the entire 124-week treatment period, this sample size will provide CCI

CCI. If the active LY3372689 treatment arm progression rate is not different than the placebo treatment arm rate, the probability of passing the efficacy criterion specified above (i.e., false positive) is approximately 2.4% CCI. The simulation for the power calculation and sample size determination was carried out in the statistical program R, version 3.6.3

6. Appendices

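### The N(0, 0.25) prior on log(DPR) is mildly informative, so the SAP's statement that no prior matters is wrong for the one parameter in the 0.6 success rule

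*SAP*

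**What the plan says.** Protocol Section 9.4.2 states: "Diffuse priors will be used for the Bayesian inferences in the DPM analysis". SAP Section 4.8.1 goes further: "The precision value for the prior distribution of all parameters is set to a small value", from which it concludes that "the prior distributions on all parameters have very little impact on the posterior distributions". No parameter is excepted.

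The same section then lists the priors. The baseline mean, the placebo visit-to-visit changes and the covariate effects each get a normal prior with second argument 10^4. For the treatment effect: "A prior distribution of $N(0, 0.25)$ is assumed for the log(DPR) parameter of each active treatment arm". The SAP applies the word diffuse to the first group but not to this prior.

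SAP Section 2 sets the primary success rule as "Probability (at least 25 % slowing of disease progression with LY3372689 relative to placebo) > 0.6", for at least one active arm. That probability is read from the posterior of log(DPR). SAP Section 5 states that, with no difference from placebo, "the probability of passing the efficacy criterion specified above (i.e., false positive) is approximately 2.4" per cent; the assumptions behind it are redacted.

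**The concern.** The general statement about priors fails for the parameter that decides the primary endpoint. A reader who relies on it will take the reported DPR, its interval and Pr(DPR < 0.75) as driven by the data alone. In fact they are pulled toward DPR = 1.

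The cut-off of 0.6 is fixed, so the prior also changes how much observed slowing the rule demands and how often the rule passes when there is no effect. No analysis in SAP Sections 4.8.2 or 4.8.3 varies the prior, so the report would not show how much of the result comes from it.

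**Working it through.** **Reading of 0.25.** SAP Section 4.8.1 writes the random intercept as a normal distribution whose second argument is a squared sigma, so the second argument is a variance. Hence SD = √0.25 = 0.5 and precision = 1/0.25 = 4. The 95% prior range for DPR is exp(±1.96 × 0.5) = 0.375 to 2.66, and prior Pr(DPR < 0.75) = Φ(−0.2877/0.5) = 0.28.

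The other readings fit poorly. If 0.25 were a precision, the prior would be nearly flat, but 10^4 as a precision would make the other priors extremely tight. If 0.25 were an SD, the false-positive rate below could never exceed about 0.4%, which does not fit 2.4%.

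**Standard error s of the estimated log(DPR).** This is not given. The 2.4% cannot be reproduced forwards because its inputs are redacted, so I use it backwards. Assumptions: it refers to the 0.6 rule, for one active arm against placebo, and the estimate is normal.

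**Formulas** (prior variance v):
- Weight on the data: B = v/(v + s²), with B = 1 for a flat prior.
- Posterior SD: s√B.
- Pass if the estimated log(DPR) is below c = [ln 0.75 − 0.2533 × s√B]/B, where ln 0.75 = −0.2877 and 0.2533 is the 60% normal quantile.
- Observed slowing needed: 1 − exp(c).
- False-positive rate: Φ(c/s).
- Chance of passing at true 35% slowing: Φ((c − ln 0.65)/s).

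Setting Φ(c/s) = 0.024 gives s = 0.167 if the 2.4% was obtained with a flat prior, or s = 0.194 if it was obtained with N(0, 0.25).

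**Worked case, s = 0.194, N(0, 0.25).** B = 0.25/(0.25 + 0.0376) = 0.869; posterior SD = 0.194 × √0.869 = 0.181; c = −(0.2877 + 0.2533 × 0.181)/0.869 = −0.384; needed slowing = 1 − exp(−0.384) = 31.9%; false-positive rate = Φ(−0.384/0.194) = 2.4%.

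| s | Prior | Shrinkage 1 − B | Slowing needed | False-positive rate | Pass at true 35% |
|---|---|---|---|---|---|
| 0.167 | flat | 0 | 28.1% | 2.4% | 0.73 |
| 0.167 | N(0, 0.25) | 10% | 30.5% | 1.5% | 0.65 |
| 0.194 | flat | 0 | 28.6% | 4.1% | 0.69 |
| 0.194 | N(0, 0.25) | 13% | 31.9% | 2.4% | 0.60 |
| 0.11 | flat | 0 | 27.1% | 0.2% | 0.85 |
| 0.11 | N(0, 0.25) | 5% | 28.1% | 0.1% | 0.82 |

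Variance 100 gives the same figures as the flat prior to within rounding.

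**Check with the DPM itself.** The model was fitted on a grid to 20,000 simulated trials per setting. Assumptions: placebo and one active arm, 7 post-baseline visits, known compound-symmetry covariance, flat priors on the placebo changes, placebo decline of 8 to 13 points and 60 to 80 participants per arm. The residual SD was tuned so that N(0, 0.25) gives 2.4%. Going from N(0, 0.25) to a diffuse prior, needed slowing fell from 25.0% to 22.3%, the false-positive rate rose from 2.4% to about 3.8%, and the chance of passing at true 35% slowing rose from 0.78 to 0.85. The absolute levels differ from the table, because flat priors on the placebo changes themselves pull toward slowing. The gap between priors, 2.7 points, agrees with the 2.4 and 3.3 points in the table.

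**The case against.** The prior is openly pre-specified, covers DPR from 0.375 to 2.66, and is never itself called diffuse. Setting 0.25 against 10^4 proves nothing, because one is on a log-ratio scale and the others on iADRS points. Prior-free spline and MMRM estimates are planned. All of this is fair. None of it makes the statement about all parameters true, and none of it shows how the prior affects the 0.6 rule.

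Three stronger readings are tempting and are not supported:
- **That the prior wastes power.** The lower chance of passing is the counterpart of a lower false-positive rate. In the normal approximation, both posteriors are monotone functions of the same estimate. At s = 0.194, N(0, 0.25) with cut-off 0.6 is the same test as a flat prior with cut-off Φ((−0.2877 + 0.3838)/0.194) = 0.69. No information is lost.
- **That shrinkage reaches 20%.** That needs s = 0.25, at which the false-positive rate would be 8.0% (flat) or 4.3% (N(0, 0.25)). Neither matches 2.4%.
- **That the graphical test is distorted.** SAP Section 4.9.2.1 sets its thresholds by null simulation with the Section 4.8.1 model, without covariates, so the same prior is largely absorbed there.

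Nor can it be said that the rule is harder to meet than the plan states: no visible text gives a required slowing, and the 2.4% may already include this prior.

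**Conclusion.** The point holds as a wrong statement about the primary analysis, with a moderate numerical effect. At the standard errors that fit the stated 2.4%, the prior shrinks log(DPR) by 10–13% and adds 2.4 to 3.3 points to the observed slowing needed. It lowers the 0.6 rule's false-positive rate from 2.4% to 1.5%, or from 4.1% to 2.4%, depending on which prior produced the 2.4%. If s were about 0.11, shrinkage would be only about 5% and the plan's wording would be close to fair.

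The direction does not depend on s: a prior centred on no effect makes the fixed rule stricter, so a reader should not infer type I error inflation. The consequence is confined to the 0.6 rule and the reported posterior DPR and probabilities. The size rests on the assumed s, on the normal approximation, and on the 2.4% belonging to the 0.6 rule for a single comparison.

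**What to change.** In SAP Section 4.8.1:
- State that 0.25 is a variance.
- Except log(DPR) from the claims that all priors have small precision and hardly matter, and describe its prior as mildly informative and centred on no effect.
- State the observed slowing that the 0.6 rule requires and its false-positive rate under this prior, from the sponsor's own simulation inputs.

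In Section 4.8.2, add a pre-specified fit with a diffuse log(DPR) prior, for example variance 100. Together this costs a few lines and one extra model fit.

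The sponsor could instead make the diffuse prior primary, to match the protocol. That is a trade-off and not a plain correction: with the 0.6 cut-off unchanged at s = 0.194, the false-positive rate would move from 2.4% to 4.1% (about 3.8% in the grid check). That rate would have to be re-derived and restated, and the Section 4.9.2.1 threshold simulation would have to use the same prior.
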